**Rationale**

A disease called *Amyotrophic lateral sclerosis* (or ALS), which leads to difficulty swallowing, breathing, and movement, has been found to be higher for those serving in the military than in the general population. There are approximately 4,200 Veterans with ALS and roughly 1,000 new cases each year. When doctors attempt to determine the degree to which an ALS patient is suffering from the disease, they apply tests that are "graded" by experts. However, this approach to testing patients may not be very accurate. Researchers aim to use a system called DESIPHER to "listen" to ALS patients and find speech mistakes related to their condition. Researchers believe that, by detecting different types of errors, DESIPHER serves as a new kind of indicator of medical problems such as difficulty breathing or swallowing, without human "grading". This may also lead to a better electronic system for understanding ALS patients' speech, even with lots of errors.

Hypotheses: Using a longitudinal study of Veterans with recently diagnosed with ALS, we propose to test the following two hypotheses:

H1: Automatic speech recognition can be achieved for ALS patients, whose speech diverges from a baseline, as established from transcribed speech data, using speech-model adaptation.

H2: Divergence of speech from baseline will serve as a marker for disease progression.

Specific Aims: Research questions to be addressed by this study are:

Q1: Is it possible to train a speech recognition system to adapt to increasingly more frequent language/speech errors of particular types, to produce an accurate textual transcript that would be readable by a caregiver or physician?

Q2: Are specific changes in physiological functioning (Forced Vital Capacity, tongue

strength, speech velocity, weight loss, aspiration risk, or psychological distress) associated with different types of language/speech errors?

**Significance:** Results of the proposed study are expected to improve our ability to appropriately identify and intervene when Veterans with ALS are at risk of serious adverse medical issues such as respiratory failure and aspiration. Detection of speech divergence may serve as an additional assessment tool that requires much less effort from the patient than existing clinical measures. A future study may incorporate the divergence voice software into common technology to prolong the Veterans' ability to use their natural voice to control the environment around them. A further study may investigate if monitoring changes in language divergence, which indicate disease progression, could improve timely access when further appropriate interventions might be indicated.

**Relevance:** In 2008, Amyotrophic lateral sclerosis (ALS) or Lou Gehrig's Disease became a presumptively compensable (service connected) disease as the Institute of Medicine (IOM) Committee stated an association between the development of ALS and military service. According to the IOM report, military service increases life risk of ALS by 1.5 fold. There are approximately 4,200 Veterans with ALS and roughly 1,000 new cases each year. At the Tampa VA, since 2007, there has been a consistent rise in the number of Veterans diagnosed and treated with ALS.

## **Background**

Amyotrophic Lateral Sclerosis (ALS) is a rapidly progressive, neurodegenerative disease that involves upper and lower motor neurons and is the most common form of motor neuron disease. ALS is characterized by muscle atrophy, muscle weakness, muscle spasticity, hyperreflexia, difficulty speaking (dysarthria), difficulty swallowing (dysphagia), and difficulty breathing (dyspnea). A serious healthcare crisis is emerging from the lack of capacity to support ALS sufferers, who typically must rely on a caregiver (often a family member) to manage their daily activities and to assist in relaying information between medical professionals and the patient. Mean survival time is three to five years; however, death may occur within months, or survival may last decades.

There are a number of standardized objective assessments of bulbar function in patients with ALS (Green et al., 2013); for example, breathing patterns, articulatory patterns, and voice loudness. These are generally measured by technologies that record chest wall movements, oral pressures and flows, oral movement and strength, and speech acoustics. However, these measures are focused on the *form* of speech output (e.g., hypernasality) rather than the *content* of the speech output in terms of dialectal variations. Identifying such variations is contextually similar to detecting different accents and dialects in spoken English.

Our speech research focuses on the detection of dialectal variations by identifying spoken language *divergences* along a range of different dimensions. We borrow the notion of divergence from the study of cross-linguistic variations (Dorr, 1993, 1994;

Dorr et al., 2002; Habash and Dorr, 2002), where a language is considered "close" to another language if it shares certain properties (but possibly not others), and "far" (i.e., *divergent*) if very few properties are shared. To illustrate the concept of divergence across languages, consider three properties: vocabulary, pronunciation, and syntactic structure. Table 1 shows the properties that are shared between Spanish and four other languages. The most radically divergent pair in the table is Spanish and Chinese, which do not share vocabulary, syntactic structure, or pronunciation. We note that one could apply the same sort of analysis within a single language, such as English, by examining different dialectal variations. For example, a native U.S. English speaker from Massachusetts is likely to pronounce certain terms like "car" in a way that is more closely aligned to the British English pronunciation (where the "r" is dropped – non-rhotic) than to that of a native U.S. English speaker from Alabama (rhotic).

**Table 1: Linguistic divergence across languages**

Spanish	Portuguese	French	English	Chinese
Vocabulary	X	X	X	
Syntactic structure	X	X		
Pronunciation	X			

We propose to apply this same notion of *divergence* to the problem of "speech functioning," constraining our language pair to asymptomatic English speech compared to impaired English speech. In this case, the properties to be studied are finer grained than the ones shown in Table 1, in that they are aligned with articulatory patterns in speech. Although we expect speech divergences to develop independently of language accent and dialect, we expect that prior work on dialect adaptation (Lehr et al., 2014) will be relevant for tracking speech divergences even within a single language. Research on modeling non-native or dialectal speech (Livescu and Glass, 2000) is a close approximation to what we propose for recognition of speech changes over time, though the focus of dialectal modeling is on detecting divergent content, not on discerning characteristics of the speech signal. In order to test our hypothesis that divergence from a baseline serves as a marker for disease progression (and that, in fact, specific speech properties vary systematically in impaired speech), the current proposed pilot is for native speakers only; this allows for variability in dialect, but not variability regarding the level of knowledge of the language, thus retaining only one variable: the level of progression of the disease over time. However, an important follow-up study is that of speech recognition of accented (non-native) speech, once the properties that vary systematically with disease progression have been carefully identified in this current pilot study.

A significant aspect of the proposed work is the identification of possible speech-related biomarkers to be examined for correlations with other aspects of physiological function. Some that have been published in the literature (e.g., Duffy, 2012; Rudzicz et al., 2014) that are relevant to dialectal variations, but have not heretofore been measured objectively through dialectal analysis, are those listed below:

- Imprecise consonants
- Distorted vowels
- Slow rate
- Short phrases
- Hypernasality
- Continuous voicing
- Distorted substitutions or additions

Table 2 is a notional table illustrating a range of articulatory properties for "baseline" English (as determined for a native English speaker who has no speech impairment, i.e. pre-symptomatic) compared to those exhibited during different stages of ALS—early, mid, late—thus providing a framework for capturing the degree of divergence. The final column has the highest level of divergence from the baseline: imprecise consonants, distorted vowels, and continuous bilabials.

**Table 2: Articulatory divergence across stages of ALS**

"Baseline" English	ALS English (early)	ALS English (mid)	ALS English (late)
consonants	imprecise	imprecise	imprecise
vowels	~baseline	distorted	distorted
bilabials (b,m)	~baseline	~baseline	hypernasal

Biadsy et al. (2011) conducted a speech processing study similar to our divergence approach, investigating the variation of speech properties under intoxicated and sober conditions. Rudzicz et al. (2014) employed another approach for recognizing impaired speech for detection of Alzheimer's, and Little (2012) developed an analogous application for detection of Parkinson's, as reported by Kepes (2014). These approaches measured the voice signal to answer a yes/no question (presence or absence of impairment), rather than analyzing the signal to determine the degree of divergence from a baseline. Nevertheless, the incidental but significant discovery from these studies, as well as related work of Beukelman et al. (2011), Green et al. (2013), and Orimaye et al. (2014)—that *pronunciation varies systematically within categories of speech impairment*—is a critical finding that can be leveraged for correlating the divergence from baseline English to different stages of ALS (i.e., the degree of biophysical degradation).

A large part of our investigation will involve the characterization of divergence types, most notably: pronunciation divergences (articulatory and acoustic distinctions) and discourse divergences (word choice, duration of utterances, and disfluencies). Table 3 illustrates these distinctions using examples of divergent speech characteristics that have been reported by Duffy (2012). In our proposed pilot study, we would expect to parameterize some—but perhaps not all—of these characteristics, as we have reports from clinician partners conducting a pilot study on ALS patients that phenomena such as these are common in the data they have collected so far (which will form our initial dataset, as described in Data Collection Protocol).

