**Table 3: Examples of Divergent Speech Characteristics**

Level	Speech Characteristics	Example	Comparable ALS Utterance	Divergence Dimensions
Pronunciation	Vowel	I wrote to the owner	I wr[aw]t to the	Substitution of back vowels

	distortion		[ooh]ner (oh/aw, oh/ooh) for front vowels
	Involuntary Repetition	The best part of the movie was the surprise ending.	[The bbbbest thing] * the best thing I wanted to tell you is...
	Imprecise consonants	The blue shirt didn't feel comfortable.	I wasn't comforful in that shirt. Deletion of soft alveolar stop ([t]/[d])
Discourse	Short phrases	I don't feel like a very accomplished chef, although I've made eggplant parmesan.	So how do you make this soup? Well I'm not so sure. See I don't know if I'd go that far. Short discourse words (so, well, see), small number of words per sentence, omission of large content words
	Slow rate	I take pride in being able to cook myself.	Um I do uh some uh cooking myself. Number of words per minute, frequency and pattern of unfilled or filled pauses (um, uh).
	Disfluencies	I walked the dog to the store.	I saw [the dog] * I mean the cat . Substitutions, possibly edited, e.g., I mean, sorry, excuse me, rather

By understanding how speech deterioration correlates with other physiological degradation, it may be possible to apply a new, non-invasive measure for assessing the functionality of an ALS patient. In addition, the features associated with speech deterioration enable the adaptation of existing speech recognition software to a patient's speech as it evolves over time, so that the quality of life for patients may be improved through conversation with a computer.

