Potential participants will be screened and evaluated for *Amyotrophic lateral sclerosis* (or ALS) within the Tampa VA systems of care. After screening a letters will be mailed about the study to these potential participants. For those who respond to the letter showing interest in participating in the study and who are eligible, an appointment will be scheduled to meet for the consenting and enrollment process. There will be Waiver of document; for control 20 healthy subjects without a diagnosis of ALS. Script for waiver of Documentation will be used to recruit the 20 healthy subjects.

This information will be extracted by the Research Assistant from participants' medical records on a quarterly basis:

1. Forced Vital Capacity (FVC),
2. Penetration-Aspiration Scale (a paper-pencil screen; Rosenbek, 1996),
3. ALSFRS-R (Cedarbaum, 1999), and
4. Speech Intelligibility Test (SIT; Beukelman et al., 2007).
5. Ba repetition test ( Rong et al., 2015).

If any measurements are missing, the research assistant will confirm collection of clinical measurements and coordinate with the clinical team.

The research assistant will measure tongue strength using the Iowa Oral Performance Instrument (IOPI Medical, Redmond, WA), and speech recordings made of four preselected passages. These passages, selected from the Texas-Instrument/MIT (TIMIT) corpus (Garofolo et al., 1993), combat what would generally lead to unintelligibility in speech recognition by providing a "ground truth"; with the knowledge of what the sentence is in advance, even if the patient is not otherwise able to speak intelligibly, the speech recognition system can be appropriately calibrated to expect certain levels of deviation from a baseline. And, the 'Ba' repetition test ( Rong et al., 2015). The diadochokinetic (DDK) rate test in which the participants were asked to clearly and rapidly repeat /ba/ was used in (Rong et al. 2015), to help with speech intelligibility deterioration as a result neurologic atrophy. While this pilot study focuses on speech recognition that accommodates varying levels of impairment, in later stages of the disease, adaptive speech recognition technology would be most useful in combination with alternative and augmentative communication (AAC) technologies and brain computer interfaces (BCI); this powerful combination would accommodate typing, gaze, and head-mouse input, in addition to speech input (see related discussion in Dorr et al., 2015).

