### **Risk/Benefit Assessment**

There are minimal risks to the subject. The subject could fatigue, in which case they would be allowed to rest until they were ready to continue. Subjects could become frustrated while reading the passage. In that case, subjects would be given a break, and then continue with the protocol. There are no known benefits to participating in this research study.

The etiology of ALS frequently creates other health issues. These anticipated issues that may require medical intervention and hospitalization include, but are not limited to:

- Respiratory Insufficiency
- sleep apnea
- malnutrition
- dehydration
- tracheotomy
- frontotemporal dementia
- falls

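### Do scripted recordings defeat the plan to characterise discourse divergence, given that word choice and sentence length are fixed by the text being read?

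*Protocol*

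**What the plan says.** The Background, in the text after Table 2, divides divergences into a pronunciation group and a discourse group. The second is given as "discourse divergences (word choice, duration of utterances, and disfluencies" (the list ends there). Table 3 then gives examples. Its row on short phrases describes the divergence as "Short discourse words (so, well, see), small number of words per sentence, omission of large content words". The same paragraph limits the promise: "we would expect to parameterize some—but perhaps not all—of these characteristics". It explains that clinical partners have already seen such phenomena in pilot data, "which will form our initial dataset, as described in Data Collection Protocol".

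The Research Plan sets out what is recorded from this cohort. At each quarterly session the research assistant measures tongue strength, with "speech recordings made of four preselected passages" taken from the TIMIT corpus, and there is a test of rapid /ba/ repetition. The healthy controls do the two speech tasks once. The text is scripted so that the recogniser can be calibrated "with the knowledge of what the sentence is in advance, even if the patient is not otherwise able to speak intelligibly". The Risk/Benefit Assessment confirms that the task is reading: "Subjects could become frustrated while reading the passage". No conversational, picture-description or other unscripted task is described.

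**The concern.** Word choice is the first discourse divergence named, and a person reading a set sentence does not choose the words. Nor does that person decide how long the sentence should be. Table 3's own example of short phrases is a fragment of self-generated conversation, which a reading task would not elicit. The Background therefore appears to announce two markers that the data collection cannot deliver.

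If so, two things would be at stake. A reported result on discourse divergence under H2 or Q2 could be taken to mean that patients simplify what they say as the disease advances, when the recordings show only how they read a given text. The loss would also be permanent, because no later analysis can recover spontaneous vocabulary from read speech. The Background also describes the properties to be studied as finer than those of Table 1, "in that they are aligned with articulatory patterns in speech", which might suggest that the document is unsure whether word choice is in scope at all.

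**Working it through.** The protocol gives no power, effect size or variance that bears on this point. The check sets each named feature against the recorded tasks.

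**Step 1: the three discourse types in the Background.**
- Word choice: fixed by the script if it means free choice. Inserted, omitted or substituted words can still be seen against the known text.
- Duration of utterances: measurable from the recording.
- Disfluencies: measurable as they occur in reading.

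So one of three is fixed, and only on the reading that word choice means free choice. The protocol does not use the word free.

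**Step 2: the dimensions in Table 3's discourse rows.**

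| Row | Dimension | In read TIMIT text |
|---|---|---|
| Short phrases | short discourse words | scored as insertions |
| Short phrases | words per sentence | planned length fixed |
| Short phrases | omitted content words | scored as omissions |
| Slow rate | words per minute | measurable as written |
| Slow rate | filled and unfilled pauses | measurable as written |
| Disfluencies | substitutions | scored against the script |

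Count: 3 + 2 + 1 = 6 dimensions. Two are measurable as written and three as departures from the script, so 2 + 3 = 5 of 6 survive. The sixth is fixed only as planned length, because insertions and omissions change the number of words actually produced. The three pronunciation rows (vowel distortion, involuntary repetition, imprecise consonants) are untouched.

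**Step 3: what the hypotheses and questions need.** H1 and Q1 concern recognition of impaired speech, for which a known text is an advantage. H2 concerns divergence from baseline as a marker of progression and names no particular feature. Q2 relates types of language or speech error to physiological measures, and errors are defined by comparison with what should have been said. None of the four requires free vocabulary or sentence length.

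**Step 4: the apparent inconsistency of scope.** The phrase about articulatory patterns contrasts the level of detail with Table 1. The list of candidate biomarkers that follows it in the same section includes slow rate, short phrases, and substitutions or additions. The section is therefore not confined to articulation, and no contradiction can be drawn from it.

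**Step 5: the cost of adding unscripted speech.** Inputs from the protocol: 20 Veterans, 8 visits, 20 controls recorded once, two annotators. Samples, as an upper bound with no death or drop-out: 20 × 8 + 20 × 1 = 180. The protocol gives no sample length or annotation speed, so both are assumed here:
- 1 minute per sample and 5 to 10 minutes of work per audio minute: 180 × 2 × 5 = 1,800 minutes = 30 hours, up to 180 × 2 × 10 = 3,600 minutes = 60 hours.
- 0.5 minute per sample at the lower speed ratio: 90 × 2 × 5 = 900 minutes = 15 hours.
- 2 minutes per sample at the higher ratio: 360 × 2 × 10 = 7,200 minutes = 120 hours.

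These figures exclude arbitration of disagreements between annotators.

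**The case for a change.** The best argument for a change is that what is recorded is settled in the protocol, so this cannot be left to an analysis plan. The sentence that names word choice carries no hedge of its own. The hedge that follows leaves open which characteristics will be used but does not say that the task rules any of them out. Short phrases also appear in the Background among the candidate biomarkers to be correlated with physiological function, which comes close to Q2. A line on scope would cost nothing and would prevent a misreading.

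Part of this stands. Free vocabulary and planned sentence length are not observable in the quarterly and control recordings, and an author who claimed otherwise would be wrong. But the line would only record how words are to be scored against a text already known. Analysts would have to do that anyway, and the protocol already provides for annotation guidelines and two independent annotators. Short phrases can still be described from pauses, omissions and rate in read speech. How to define them is a matter for those guidelines.

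The pilot dataset also limits the argument. Its speech task is not described, so it cannot be said that discourse features are beyond the whole project, only that some are beyond these recordings.

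**Conclusion.** The observation is true and the plan can stand. At most one of the six discourse dimensions in Table 3 is fixed by the script, and none of the pronunciation rows is affected. No hypothesis or question rests on the missing feature, and following the plan as written gives sound error scores against a known text.

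The choice of scripted speech is a reasoned trade-off. It gives up self-chosen language in return for a reference text that remains usable when speech can no longer be understood. An unscripted sample would be sparse and hard to transcribe in late disease, just where the reference text is most useful. It would also add up to 180 samples and, on the assumptions above, 30 to 60 hours of annotation (15 to 120 across the full assumed range).

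The conclusion assumes that discourse results from the quarterly and control recordings will be reported as departures from the scripted text and not as changes in what patients choose to say. Authors may say so in a sentence if they wish. That clarification is optional and should not extend to the pilot dataset, whose speech task is unknown.

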**Table 3: Examples of Divergent Speech Characteristics**

Level	Speech Characteristics	Example	Comparable ALS Utterance	Divergence Dimensions
Pronunciation	Vowel	I wrote to the owner	I wr[aw]t to the	Substitution of back vowels

	distortion		[ooh]ner (oh/aw, oh/ooh) for front vowels
	Involuntary Repetition	The best part of the movie was the surprise ending.	[The bbbbest thing] * the best thing I wanted to tell you is...
	Imprecise consonants	The blue shirt didn't feel comfortable.	I wasn't comforful in that shirt. Deletion of soft alveolar stop ([t]/[d])
Discourse	Short phrases	I don't feel like a very accomplished chef, although I've made eggplant parmesan.	So how do you make this soup? Well I'm not so sure. See I don't know if I'd go that far. Short discourse words (so, well, see), small number of words per sentence, omission of large content words
	Slow rate	I take pride in being able to cook myself.	Um I do uh some uh cooking myself. Number of words per minute, frequency and pattern of unfilled or filled pauses (um, uh).
	Disfluencies	I walked the dog to the store.	I saw [the dog] * I mean the cat . Substitutions, possibly edited, e.g., I mean, sorry, excuse me, rather

By understanding how speech deterioration correlates with other physiological degradation, it may be possible to apply a new, non-invasive measure for assessing the functionality of an ALS patient. In addition, the features associated with speech deterioration enable the adaptation of existing speech recognition software to a patient's speech as it evolves over time, so that the quality of life for patients may be improved through conversation with a computer.

